10.2 Secondary study parameters

Hypothesis 2 “Girls in the intervention group will have less dyadic depression contagion during the intervention period, immediately after the intervention period and after one-year follow-up, relative to girls in the control condition” will be tested using discrete-time survival analysis and via actor-partner interdependence modeling (Cook & Kenny, 2005), respectively.

We will use prospective change, actor-partner interdependence modeling (APIM) to investigate whether dyads in the intervention condition will experience less dyadic depression contagion compared to dyads in the control arm from T0 – one-year after follow up APIM allows to test the effects of each girl's predictor variables (here: depressive symptoms) on her own outcomes (actor effects) and on her friend's outcomes (partner effects), while controlling for similarities between dyad-members. If the actor effect is non-significant, this indicates stability in depression symptoms. If the actor effect is significant, this indicates contagion between girls in the dyad. We will use multi-group comparisons to test whether contagion effects are less strong in the intervention arm compared to the control arm. Specifically, a model in which the actor and partner effects will be estimated freely for the intervention and control arm (unconstrained model) versus a model where the actor and partner effects will be constrained to be equal will be specified. If constraining the parameters to be equal results in poorer model fit, this indicates that effects are not similar in the two conditions.

Hypothesis 3 “Girls in the intervention group will demonstrate b) less dyadic anxiety contagion during the intervention period, immediately after the intervention period and after one-year follow-up, relative to girls in the control condition” will be tested using LGM, DTSA and multi-group APIM, respectively.

Multi-group (i.e., intervention versus control condition) APIM will be used to investigate whether dyads in the intervention condition will experience less anxiety contagion compared to dyads in the control arm from T0 to one-year after follow-up. For a more detailed description of this model, please see the model description in hypothesis 2.

Hypothesis 4 “Girls in the intervention group will experience better friendship quality, higher levels of positive affect and higher levels of interpersonal responses to positive affect during the intervention period, immediately after the intervention period and after one-year follow-up, relative to girls in the control condition” will be tested using multi-level LGMs for each outcome, respectively.

Three multi-level LGMs with intervention arm as the exogenous predictor variable and growth rate of friendship quality, positive affect and interpersonal responses to positive affect as the (potentially correlated) outcome variables, will be used to test whether girls in the intervention arm experience more improvements in friendship quality, a faster growth in positive affect and faster growth levels of interpersonal responses to positive affect, compared to girls in the control arm. The outcome variables will be modelled on both the individual (within) level and

on the dyadic (between) level. This way, the between-level intervention effects will be adjusted for variation between individuals in the outcome measures on the within-level. Note that we have no a priori hypotheses regarding the nature of the growth patterns of the outcome measures and that it may best be captured by either a linear or a non-linear slope. We will adjust the analysis accordingly.

Hypothesis 5 “The hypothesized intervention effects on co-rumination (primary outcome) will be mediated by the development of mindfulness and emotion regulation skills during the intervention period, immediately after the intervention period and after one-year follow-up” will be tested using a multi-level parallel process LGMs for self-reported co-rumination.

For the model where co-rumination is measured via self-report, a multi-level (LGM) model, with intervention arm as the exogenous predictor variable, growth rate of mindfulness and emotion regulation skills as the mediating variables and growth rate of co-rumination as the primary outcome variable. The mediator and primary and secondary outcome variables will be modelled on both the individual (within) level and on the dyadic (between) level. This way, the between-level intervention effects will be adjusted for variation between individuals in co-rumination (primary outcome), internalizing symptoms (depression/anxiety, secondary outcomes) and negative affect (secondary outcome) on the within-level. Note that we have no a priori hypotheses regarding the nature of the growth patterns of the mediator and outcome variables and that they may be best captured by either a linear or a non-linear slope. We will adjust the analysis accordingly.

Hypothesis 6 “Girls in the intervention group will experience greater feelings of self-worth and will show less health care use, immediately after the intervention period and after one-year follow-up, relative to girls in the control condition” will be tested using multi-level LGMs for each outcome, respectively.

Two multi-level LGMs with intervention arm as the exogenous predictor variable and growth rate self-worth and health care use as the (potentially correlated) outcome variables, will be used to test whether girls in the intervention arm experience more feelings of self-worth and less health care use over time, compared to girls in the control arm. The outcome variables will be modelled on both the individual (within) level and on the dyadic (between) level. This way, the between-level intervention effects will be adjusted for variation between individuals in the outcome measures on the within-level. Please note that health care use will be modelled as a categorical LGM due to the nature of the data (dichotomous). Furthermore, note also that we have no a priori hypotheses regarding the nature of the growth patterns of the outcome

measures and that it may best captured by either a linear or a non-linear slope. We will adjust the analysis accordingly.

Statistical software

All analyses will be conducted in structural equation modeling program Mplus (v 8.7 or higher; Muthén and Muthén, 1998-2017). Model fit will be determined using the comparative fit index (CFI, critical value $\geq .95$), the root mean square error of approximation (RMSEA, critical value $\leq .06$) and the standardized root mean square residual (SRMR, critical value $< .08$; Hu & Bentler, 1999). When appropriate, standard errors will be adjusted for clustering of dyads within schools using a sandwich estimator (Williams, 2000). For hypotheses that include mediation analysis (hypothesis 1 & 5) we will use 10.000 bootstrap resamples with replacement and bias-corrected 95% confidence intervals to test these indirect effects (Preacher and Hayes, 2004). When appropriate, differences in (indirect) pathways between the intervention and the control arm will be estimated using the DIFFtest option in Mplus (when using the WLSMV estimator) or the Satorra Bentler chi-square difference test (Satorra & Bentler, 2001; when using the MLR estimator).

Handling of protocol non-adherence and missing data

The way the questionnaires are administered online makes it impossible to skip a question. Participants who do not complete a questionnaire will receive one or more reminders. Missing data during the follow-up period (e.g., due to unavailability during a certain measurement wave or due to dropout) will be handled using Full Information Maximum Likelihood (FIML) estimation.

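### Section 10.2 reads the actor effect as contagion although it defines contagion's path as the partner effect, and its joint arm comparison does not isolate that path (Hypotheses 2 and 3)

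*Protocol*

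**What the plan says.** Section 10.2 tests Hypothesis 2 with a prospective-change actor-partner interdependence model (APIM), from T0 to the one-year follow-up. It describes one set of paths running from a girl's symptoms "on her own outcomes (actor effects") and another "on her friend's outcomes (partner effects"). Two reading rules follow. The first is "If the actor effect is non-significant, this indicates stability in depression symptoms". The second is "If the actor effect is significant, this indicates contagion between girls in the dyad". No rule is given for the partner effect.

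The arms are then compared by multi-group modelling. A model with actor and partner effects free in each arm is set against "a model where the actor and partner effects will be constrained to be equal". The stated purpose is to see whether contagion is weaker under the programme. Poorer fit of the constrained model is read only as showing that the effects differ between conditions.

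Hypothesis 3 uses the same model for anxiety: "For a more detailed description of this model, please see the model description in hypothesis 2".

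**The concern.** Contagion within a friendship means that one girl's symptoms predict her friend's later symptoms. Under the protocol's own definitions that is the partner path. A path from a girl to herself cannot show spread to someone else, so the contagion rule is attached to the wrong path.

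Two consequences follow. First, depression and anxiety scores usually persist to some degree, so a literal reading would report that ordinary persistence as contagion. Where persistence is absent, the rule would miss real contagion. Second, the arm comparison moves both paths at once, so poorer fit may come from a difference in stability alone. Section 10.2 names no separate test of the path that Hypotheses 2 and 3 concern.

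**Working it through.** **1. Definitions against rules**

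| Path | Definition in 10.2 | Reading given in 10.2 | Reading that follows from the definition |
|---|---|---|---|
| Actor | girl to herself | significant = contagion; not significant = stability | stability (later score as outcome) |
| Partner | girl to her friend | none | contagion |

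Nothing elsewhere in the protocol corrects this.

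**2. Does the form of the outcome matter?** Write a girl's later score as y₁ = a·x₁ + p·x₂ + e, where x₁ is her own baseline score and x₂ her friend's, so a is the actor path and p the partner path. If the outcome is the raw change, y₁ − x₁ = (a − 1)·x₁ + p·x₂ + e. The actor coefficient becomes a − 1, while the partner coefficient is still p. Contagion is the partner path under either form.

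**3. Size of the misreading.** The protocol states no figure for this analysis, so there is none to reproduce. Inputs from section 4.4 are alpha 0.05 (taken as two-sided; sidedness is not stated), ICC 0.40 between friends, and 122 to 160 dyads, that is 61 to 80 per arm. Assumptions not in the protocol are standardised scores, exchangeable girls, residual within-dyad correlation 0.2, stability a of 0.3 to 0.7 and contagion p of 0 to 0.3. Each scenario was simulated 4,000 times, and the single-path tests were read within one arm.

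Hand check: the residual variance is v = 1 − a² − p² − 2ap(0.40), and the variance of the estimated actor path is k·v/n, with k = ¼[(1.2/1.4) + (0.8/0.6)] = ¼(0.857 + 1.333) = 0.548. For a = 0.3 and p = 0, v = 0.91.
- n = 61: SE = √(0.548 × 0.91/61) = 0.090; z = 0.3/0.090 = 3.3; probability of significance about 0.91.
- n = 80: SE = √(0.548 × 0.91/80) = 0.079; z = 3.8; about 0.97.

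Simulated results (61 / 80 dyads per arm):

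| Scenario | Written rule (actor) | Partner effect |
|---|---|---|
| a = 0.3, no contagion | 90% / 96% | 5.4% / 4.7% |
| a = 0.5, no contagion | 100% / 100% | 5.4% / 5.6% |
| a = 0.7, no contagion | 100% / 100% | 5.0% / 5.2% |
| a = 0, contagion 0.3 | 5.9% / 4.8% | 90% / 96% |

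With raw change as the outcome and no contagion, the actor effect is still significant in 99–100% of runs for a of 0.3 to 0.7, because a − 1 is far from zero.

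**4. Joint arm comparison.** The covariance term is ¼(0.857 − 1.333) = −0.119. For a difference of 0.2 in stability alone, the 2-df noncentrality is n × 0.2² × [0.548/(0.548² − 0.119²)]/(v₁ + v₂) = n × 0.04 × 1.917/(v₁ + v₂).
- No contagion, a = 0.6 versus 0.4: v₁ + v₂ = 0.64 + 0.84 = 1.48. The noncentrality is 3.16 (n = 61) and 4.14 (n = 80), giving rejection of about 34% and 43%. Simulated: 34% and 43%.
- Contagion 0.10 in both arms, same stability gap: v₁ + v₂ = 0.582 + 0.798 = 1.38. The noncentrality is 4.44 (n = 80), giving about 46%. Simulated: 45–46%.

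| Scenario | Joint test | Partner-only test |
|---|---|---|
| Equal stability (0.3, 0.5 or 0.7), no contagion | 4.9–5.6% | 4.9–5.7% |
| Stability 0.6 vs 0.4, no contagion (61 / 80) | 34% / 43% | 5.2% / 4.8% |
| Stability 0.7 vs 0.4, no contagion (61 / 80) | 70% / 82% | 5.5% / 5.7% |
| Stability 0.5, contagion 0.3 vs 0 (61 / 80) | 71% / 83% | 78% / 88% |
| Stability 0.5, contagion 0.2 vs 0 (61 / 80) | 36% / 46% | 43% / 53% |

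**The case against.** **A slip of the pen.** The second rule probably meant the partner effect, and the correct definitions stand just before it. That is likely, but changing that one word leaves the first rule in place and the arm comparison unrepaired. A pre-specified rule should not have to be guessed.

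**The prospective-change wording.** With a raw change score, a non-significant actor effect would mean that a cannot be told apart from 1, which is one sense of stability. This could lend the first rule some meaning. It does not rescue the contagion rule, since the partner path is p in either form. It does limit the remedy: calling the actor effect stability is safe only once the outcome is stated to be the later score.

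**The arm comparison.** A reader might infer that it tests the wrong parameters. The text does not support that: the partner path is among those freed and constrained. The stated aim is also directional, and the free model shows the sign in each arm. A reader might further infer that poorer fit would be credited to the programme as reduced contagion. The protocol says only that the effects then differ, so that step is not in the text. What stands is that the joint test does not isolate contagion. Follow-up constraints on single paths could be left to a statistical analysis plan, but the misstated reading rule is in the protocol itself.

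**The figures.** The 90–100% is the power of a stability test at assumed values. It shows what literal use would do and is not evidence of a separate harm. The stability gaps between arms are also assumed. For a real contagion difference, the power lost to the joint test is modest, about 5 to 8 percentage points in the scenarios run.

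**Conclusion.** The reading rule is wrong as written, by the protocol's own definitions, and Hypothesis 3 inherits it. This conclusion needs no simulation.

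The size depends on assumed stability, contagion and residual correlation. With zero contagion, literal use reports contagion in about 90–100% of trials, against about 5% from the partner effect. True contagion of 0.3 without any stability is picked up in only 5–6%, though that is an extreme case.

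The arm comparison is a lesser defect. It includes the right parameter but mixes it with another, so it can reject in about 34–46% of trials on a stability gap of 0.4 versus 0.6 with equal contagion. Where stability is equal between arms it keeps its nominal level.

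Hypotheses 2 and 3 are secondary. The primary co-rumination analysis in section 10.1 is unaffected. The rule should be corrected before the contagion analyses are run.

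**What to change.** Amend section 10.2 under Hypothesis 2, so that Hypothesis 3 inherits the corrected text:

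- State that contagion is the partner effect.
- State that the outcome is the later score, adjusted for the baseline score, and that the actor effect then reflects stability.
- In the arm comparison, leave actor paths free in each arm and constrain only the partner path to equality.
- Base Hypotheses 2 and 3 on the signed partner-path difference (intervention minus control, expected below zero), reported with its confidence interval.

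The cost is a few sentences in section 10.2. No extra data, assessments or participants are needed.

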2. OBJECTIVES

Primary Objective: The primary objective of the Girls United cluster Randomized Controlled Trial (cRCT) is to examine the effectiveness of the Girls United prevention program on self-reported co-rumination.

Secondary Objectives: The second objective of this study is to investigate the intended active mechanisms of this program, especially enhancement of mindfulness and emotion regulation skills. Furthermore, the effectiveness of the Girls United mindfulness-based prevention program on self-reported symptoms of depression and anxiety, self-reported contagion of depression and anxiety symptoms, self- and friend-reported friendship quality, self-reported positive and negative affect, interpersonal responses to positive affect, self-reported self-worth

and parent-reported health care use will be studied in Dutch young adolescent girls from age 10 to 12 years old.

The research question is: To what extent does the app-based mindfulness prevention program Happy Friends, Positive Minds impact mental health and well-being in Dutch 10-to-12-year-old girls?

Hypotheses:

- (1) Girls in the intervention group will have a greater reduction in co-rumination (primary outcome) about distress and difficult emotions and feelings, (and thereby) internalizing symptoms (depression/anxiety, secondary outcome) and negative affect (secondary outcomes) during the intervention period, immediately after the intervention period and after one-year follow-up, relative to girls in the control condition.
- (2) Girls in the intervention group will have less dyadic depression contagion, immediately after the intervention period and after one-year follow-up, relative to girls in the control condition.
- (3) Girls in the intervention group will demonstrate less dyadic anxiety contagion during the intervention period, immediately after the intervention period and after one-year follow-up, relative to girls in the control condition.
- (4) Girls in the intervention group will experience better friendship quality, higher levels of positive affect and higher levels of interpersonal responses to positive affect, during the intervention period, immediately after the intervention period and after one-year follow-up, relative to girls in the control condition.

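### Protocol 10.2 names a survival analysis (Hypotheses 2 and 3) and a growth model (Hypothesis 3) as tests of contagion between friends, gives neither a friend-to-friend term, and does not say that the APIM alone decides

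*Protocol*

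**What the plan says.** Section 2 of the protocol states each contagion hypothesis as a single claim; Hypothesis 3 reads "Girls in the intervention group will demonstrate less dyadic anxiety contagion during the intervention period", then lists later time points. Section 10.2 restates Hypothesis 2 as "Girls in the intervention group will have less dyadic depression contagion during the intervention period" and says that it "will be tested using discrete-time survival analysis and via actor-partner interdependence modeling (Cook & Kenny, 2005), respectively".

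For Hypothesis 3, section 10.2 opens with "Girls in the intervention group will demonstrate b) less dyadic anxiety contagion during the intervention period" and says that it "will be tested using LGM, DTSA and multi-group APIM, respectively". The growth model (LGM) is therefore named for Hypothesis 3 only. Discrete-time survival analysis (DTSA) is named for both.

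The descriptive paragraphs cover only the APIM. Under Hypothesis 2: "We will use multi-group comparisons to test whether contagion effects are less strong in the intervention arm compared to the control arm". Under Hypothesis 3, multi-group APIM "will be used to investigate whether dyads in the intervention condition will experience less anxiety contagion compared to dyads in the control arm", with a reference back to Hypothesis 2 for the details. The survival analysis and the growth model are not described for either contagion hypothesis, and no sentence says which method decides.

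**The concern.** The null behind Hypotheses 2 and 3 is that the effect of one girl's symptoms on her friend's later symptoms is the same in both arms. A test of that null needs a term linking the two girls. Of the methods named, only the APIM is given one.

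Hypothesis 1 expects the programme to lower each girl's own internalizing symptoms. If it does, a test of onset or of symptom growth can reject although transmission between friends is unchanged. Because section 10.2 lists such tests under the contagion hypotheses without ranking them, an analyst who follows the text could report that result as less contagion. The opposite mistake is also possible: a real change in transmission that barely moves average symptoms could be missed by these tests and reported as no effect.

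**Working it through.** The plan states no figure on this point, so there is nothing to reproduce. The check is a comparison of the text, followed by an illustration.

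**1. What each named method tests, as the plan specifies it**

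| Method | Named for | Null hypothesis | Link between friends |
|---|---|---|---|
| Multi-group APIM | H2, H3 | Equal actor and partner effects in the two arms | Yes, the partner effect |
| DTSA | H2, H3 | Not described; in standard form, equal hazard of onset | None stated |
| LGM | H3 | Not described; in 10.1 and elsewhere in 10.2, no arm effect on growth rates | None stated |

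Section 10.1 already uses a growth model for internalizing symptoms under Hypothesis 1. A growth model of anxiety under Hypothesis 3 would repeat that question under another label.

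**2. The wording of the naming sentences**

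Both end in *respectively*, which needs several hypotheses or sub-hypotheses to pair with the methods. Each contains one claim. Hypothesis 3 also carries an item b) with no item a). This points to text left from longer hypotheses. The list of abbreviations likewise holds latent class and latent transition analysis, which no hypothesis uses.

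**3. Illustration of direction**

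*From the protocol:* waves T0 to T5, 1:1 allocation, at most 80 dyads per arm, correlation of 0.40 between friends, alpha 0.05 (taken as two-sided). The power calculation's minimum of 122 dyads gives 122 / 2 = 61 per arm.

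*Assumed:* actor effect 0.6; partner effect b of 0.15 or 0; residual SD 0.7 (baseline SD 1); a direct reduction of δ per wave in the intervention arm; onset defined as first reaching +1 baseline SD.

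*Model:* Y(own, t) = 0.6 × Y(own, t−1) + b × Y(friend, t−1) − δ × arm + error.

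*Tests:* arm effect on the dyad-mean slope (a simple stand-in for the growth model); discrete-time logistic hazard clustered by dyad; arm-by-partner interaction in a lagged APIM. There were 400 runs per row. Entries are the share of runs significant in favour of the intervention, so the nominal rate is 2.5%, with Monte Carlo error √(0.025 × 0.975 / 400) ≈ 0.8 points.

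| Dyads per arm | b control / intervention | δ | Approx. benefit at T4 (SD) | Slope | Survival | Arm × partner |
|---|---|---|---|---|---|---|
| 80 | 0.15 / 0.15 | 0 | 0 | 3.8% | 2.2% | 2.5% |
| 80 | 0.15 / 0.15 | 0.10 | 0.29 | 43.8% | 30.5% | 2.5% |
| 80 | 0.15 / 0.15 | 0.15 | 0.42 | 71.8% | 53.8% | 2.2% |
| 61 | 0.15 / 0.15 | 0.15 | 0.42 | 59.8% | 44.8% | 2.0% |
| 80 | 0 / 0 | 0.15 | 0.38 | 46.5% | 52.8% | 2.5% |
| 80 | 0.15 / 0 | 0 | 0 | 3.5% | 4.0% | 97.0% |

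With equal contagion, or none at all, the slope and survival tests reject because symptoms fell. With lower contagion and no direct effect (last row) they stay near the nominal rate, while the arm-by-partner test detects the change. The last row depends on scores being centred at zero, so that a weaker partner path does not move the mean.

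A second set of runs let the own-symptom effect build up to 0.3 or 0.5 SD by T4, with equal partner effects of 0.15, and counted rejections in either direction. The slope test rejected in 33–69% of trials at 122 dyads and 41–80% at 160, the survival test in 27–54% and 26–63%, and the arm-by-partner term in 5–6%. The direction is the same.

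**The case against.** The strongest reply is that the plan in effect tests contagion by APIM alone. The paragraphs that say what will be done mention nothing else, the only comparison described is the constrained against the unconstrained APIM, and the other methods look like editorial remnants. Symptom growth has its home under Hypothesis 1, so a growth effect would naturally be reported there. Most of this stands. It does not remove the point, because the current text still says that the hypotheses will be tested by the other methods and never says that the APIM decides.

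Four stronger readings are tempting, and the document does not support them:

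- *The growth model is a test of both hypotheses.* It is named for Hypothesis 3 only.
- *An ordinary treatment effect would count as less contagion.* No sentence says that a survival or growth result will be read that way. The text permits it; it does not prescribe it.
- *A survival or growth model cannot address contagion.* It could, for example with the friend's earlier status as a time-varying covariate or with paths across friends. The defect is that no such term is specified. The missing onset event is not a defect in itself, since an analysis plan may define it. Sections 8.1.2 and 9.2.2 contain possible cut-offs for the CDI-2 and RCADS, though neither is tied to a survival analysis.
- *The error rate rises to about 10% or 14%.* These are 1 − 0.95² = 9.75% and 1 − 0.95³ = 14.3%. They require independent tests and a rule that any one success suffices, and the plan states no such rule.

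It is also fair to object that the illustration shows tests of symptoms detecting an assumed effect on symptoms, and that its arm-by-partner term is not the planned test, which constrains actor and partner effects together. Both limits are accepted. The rates show direction only.

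**Conclusion.** The point holds as a mismatch between stated hypotheses and named tests. Section 10.2 lists DTSA for Hypotheses 2 and 3, and an LGM for Hypothesis 3, as tests of a contagion claim. Neither has a friend-to-friend term as specified, and the plan does not say that the APIM alone decides. A literal reader could therefore report a fall in each girl's own symptoms as less contagion.

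No single figure can be put on this risk. The rates above rest on assumed effect sizes, path coefficients and an assumed event cut-off. What DTSA and LGM would test is inferred from their standard form and from the plan's use of growth models elsewhere. The hypotheses are secondary, and the primary analysis of co-rumination is unaffected.

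**What to change.** In section 10.2, state that the between-arm difference in the partner path of the multi-group APIM is the sole test of Hypothesis 2 (depression) and of Hypothesis 3 (anxiety). Since the planned comparison constrains actor and partner effects together, the partner path should be tested on its own.

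Delete DTSA from Hypothesis 2, and DTSA and LGM from Hypothesis 3, along with *respectively* and the stray b). If onset or symptom growth is still of interest, state each as its own secondary hypothesis, with a defined event for onset, and do not present it as a test of contagion.

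While editing, align the sentence in the same section that reads a significant actor effect as contagion: the section itself defines effects on the friend as partner effects. That is a separate error, but the new wording must not conflict with it.

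The cost is wording only. No new data are needed; if the methods are deleted, there is one analysis fewer for Hypothesis 2 and two fewer for Hypothesis 3.
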